## 9. Locations of Study

VUMC/C-Saúde supports HIV care and treatment services in 149 clinical sites in the province. These sites range from small district-level hospitals to rural health posts. Our trial will involve four of these clinics (with a focus on urban facilities): 1) as a control site, 2) as a site implementing anti-stigma training, 3) as a site implementing resilience training, and 4) as a site implementing anti-stigma and resilience training.

Health facilities will be eligible for selection in the study if they serve at least 4,000 patients enrolled on ART who will be scheduled for clinic visit(s) during the study period. For study operational purposes, only HF in Quelimane City and Nicoadala districts will be considered for selection. **Table 5** below shows a list of health facilities meeting these criteria and from which study sites will be selected by study co-investigators in collaboration with DPS-Z/NIOZ study focal point. Site selection will also consider feasibility of study activities at the indicated HF.

**Table 5:** List of Health Facilities Eligible for Study Site Selection

HF Sites Eligible for Study Selection				
	District	Health facility	# of patients in Q1 (Oct – Dec 2022)	# of patients in Q2 (Jan – Mar 2023)
1	Nicoadala	CS Nicoadala	13113	12580
2	Quelimane	CS 17 de Setembro	7761	7637
3	Quelimane	CS Coalane	7074	6981
4	Nicoadala	CS Licuare	5882	6030
5	Quelimane	CS 24 de Julho	5921	5917
6	Quelimane	CS Chabeco	4698	4727
7	Quelimane	CS Namuinho	4741	4422
8	Quelimane	CS 4 de Dezembro	4180	4149

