#### **Objective 2:**

With Objective 2 most of our outcomes are continuous measurements, and analyses will be similar to those described above: linear mixed effects models that take advantage of the factorial nature of outcome, with clusters defined as study sites, and unadjusted and adjusted for a small number of PLHIV-level covariates (age, sex, educational level, marital status, language, duration on ART, and history of ART medication pick-ups within the previous 6 months). For binary outcomes (e.g., undetectable viral load), we will fit generalized linear mixed effects models with a logit link function.

Every patient is given 30, 60, 90, or 180 days to pick up their ART medication, as indicated in the medical charts. If a patient picks up medication after the indicated/scheduled date, they will be considered "non-adherent" for each day after their specific pick-up date; this will be assessed over the course of the 6-month follow-up and will be treated as a continuous variable (a proportion between 0 and 1 for each participant). Participants who are lost to follow-up from the health facility during the 6-month follow-up period will be considered "non-adherent" for the days that they are lost. For persons who die or are known to have transferred care outside of the catchment area, the proportion of time on medication will be computed using only time prior to death or transfer of care. For our primary retention outcome (proportion of time on medication), normality assumptions are unlikely to hold, perhaps even after data transformation. Hence, we will fit a cumulative probability model (CPM) with fixed effects for the clinics. The CPM is well-suited for this setting because it does not require symmetry/normality in the outcome (which is bounded between 0 and 1 and likely not normal); in the absence of covariates, it reduces to the Wilcoxon rank sum test. The CPM has been shown to perform well in settings investigating medication adherence. Specifically, the distribution of the proportion of time on medication will be modeled as

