## Appendix 9: Routinely collected clinical data of all PLHIV to be extracted from EPTS (Objective 2)

1. Age
2. Sex
3. Date of HIV diagnosis
4. Education level (highest completed)
5. Marital status
6. Number of children alive
7. HIV status disclosed to family (yes/no)
8. ART initiation date
9. ART pick up dates (all during study period)
10. Scheduled ART pick up dates (all during study period)
11. Clinical appointment dates (all during study period)
12. Scheduled clinical appointment dates (all during study period)
13. Viral Load test results and dates (all during study period)
14. Pregnancy status at time of study.
15. Differentiated model of care (all documented during study period)
16. Type of drug dispensation (all documented during study period)
17. Blood pressure (all results during study period)
18. Weight (all results during study period)
19. Height
20. TB treatment
21. WHO staging
22. patient ID
23. CD4 results and dates (all during study period)

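### The primary adherence rule leaves documented transfers inside an undefined catchment area to be scored as non-adherent, and the extraction lists name no death or transfer item with which to apply the exemption it does grant

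*Combined protocol and SAP*

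**What the plan says.** Section 8b makes adherence, measured as proportion of time on medication, part of the primary measure of effectiveness in patients. Section 10 (Objective 2) calls it the primary retention outcome and scores it as follows:

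- **Schedule.** "Every patient is given 30, 60, 90, or 180 days to pick up their ART medication". Each day past the scheduled date without a pick-up is non-adherent, and the six-month result is a continuous proportion from 0 to 1.
- **Loss.** The rule for those who leave begins "Participants who are lost to follow-up from the health facility during the 6-month follow-up period will be considered"; the status it assigns to each day lost is non-adherent.
- **Exemption.** Two groups are treated differently: "For persons who die or are known to have transferred care outside of the catchment area". Their score covers only the days before that event.

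Appendix 9 lists 23 items to extract for all patients, and Appendix 10 lists 8 for surveyed patients. Both include actual and scheduled pick-up dates. Neither includes death, transfer, patient status or a date for any of these. The description of routine data in Section 8a names none either, but it is expressly open-ended.

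On geography, Section 9 states that "only HF in Quelimane City and Nicoadala districts will be considered for selection". Table 5 lists eight eligible facilities, six of them in Quelimane.

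**The concern.** The loss rule refers to the health facility, while the exemption refers to the catchment area. A patient who moves to another clinic in the same city, with the move on record, has left the first but perhaps not the second. No sentence covers that case, so the loss rule applies by default.

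The second gap does not depend on what catchment area means. If the analyst receives only the listed fields, a death or a distant transfer looks like default: the pick-ups stop. The exemption then cannot be applied.

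The protocol itself expects movement. The survey exclusions in Section 7b mention people who get HIV care at a facility other than their own, and the waiver request in Section 11 cites records of patients who may no longer be enrolled. No rule ties a patient to one site, so someone who moves between two study sites could enter the data in two arms.

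At stake is the value of the primary patient outcome for everyone who dies or transfers. With one site per arm, a local difference in those rates could appear as a training effect or hide one.

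**Working it through.** **1. Rule against listed data**

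| Event | Scoring in Section 10 | Item in Appendix 9 or 10 |
|---|---|---|
| Late pick-up at the study site | non-adherent for the late days | scheduled and actual dates |
| Default | non-adherent for the days lost | inferred from missing pick-ups |
| Death | observation ends | none named |
| Known transfer outside the catchment area | observation ends | none named |
| Known transfer inside the catchment area | no specific rule; the loss rule applies literally | none named |

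**2. The plan's own figure, for scale**

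Section 7c gives a detectable difference of 0.64 SD with 4,000 patients per site, ICC 0.05, two-sided 0.05 and 80% power. With two sites against two, the effective number per group is 2 × 4,000 / (1 + 3,999 × 0.05) = 8,000 / 200.95 = 39.81. A two-sample t calculation on that number gives 0.636 SD, so the figure reproduces. It does not depend on the transfer rule: removing 10% of patients leaves it at 0.636.

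**3. Misscored time per affected patient**

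Assumptions: exit time T is uniform over 180 days; days to the next scheduled pick-up R are uniform over the supply length L; pick-ups elsewhere do not appear in the study site's extract. The mean share of the window scored non-adherent after exit is

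E[max(0, 180 − T − R)] / 180 = (180³ − (180 − L)³) / (6 × 180² × L)

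- L = 30: (5,832,000 − 3,375,000) / 5,832,000 = 0.421
- L = 60: (5,832,000 − 1,728,000) / 11,664,000 = 0.352
- L = 90: (5,832,000 − 729,000) / 17,496,000 = 0.292
- L = 180: 5,832,000 / 34,992,000 = 0.167

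For a patient with no earlier late days, this is the average drop in the 0–1 score.

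**4. Effect on a site mean**

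The documents give no death or transfer rate. The nearest figure is 87% in care at 12 months (Section 4). Under a constant hazard that is 1 − √0.87 = 6.7% attrition by six months. It is not split by cause, and it concerns people testing positive rather than the cohort already active in care.

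- If 5% die or transfer (assumed): 5 × 0.167 to 5 × 0.421 = 0.8 to 2.1 points off the site mean.
- If all 6.7% were deaths or transfers: 1.1 to 2.8 points.

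**5. Effect on the comparison**

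Equal rates at all sites shift every arm alike. For unequal rates (assumed gaps):

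- Gap of 1 point between the two groups of sites: 1 × 0.167 to 1 × 0.421 = 0.2 to 0.4 points.
- Gap of 5 points: 0.8 to 2.1 points.
- One site of four, equal in size, 5 points above the rest: the grouped gap is 2.5 points, giving 0.4 to 1.1 points.

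For an outcome SD of 0.15 to 0.25 (assumed), gaps of 1 to 5 points give between 0.0017 / 0.25 = 0.007 SD and 0.021 / 0.15 = 0.14 SD.

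**The case against.** **The in-area rule is an inference.** Section 10 does not say that a transfer within the catchment area is non-adherent. If the term means the facility's own area, most moves to another clinic are already exempt. This stands, and it is why the point is an undefined term and an incomplete rule rather than a stated wrong rule.

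**The field lists may not be closed.** Section 8a's list is open-ended and names items that Appendix 9 omits, among them the health facility itself, which the analysis must have. A reader might infer that deaths and transfers cannot be obtained. The documents do not support that; they show only that no listed field supplies them.

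**Moves may carry information about the intervention.** A reader might infer that transfers have nothing to do with staff behaviour. Section 7b links some care-seeking elsewhere to stigma, which the training targets. Stopping the clock at every transfer could therefore be informative censoring. This stands and calls for a sensitivity analysis.

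**The effect is small beside what the trial can detect.** The illustrated shifts are well below 0.64 SD. That is fair on size, although a small effect at the detectable-difference scale is still a preventable error in the primary outcome.

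**Conclusion.** The point holds as a should-fix. The exemption rests on an undefined term, the literal rule scores documented in-area transfers as non-adherent, and the listed extract does not identify even the deaths and transfers that the plan means to exempt.

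Per affected patient the effect is substantial: about 42%, 29% or 17% of the window at 30-, 90- or 180-day supply, given uniform exit times. Its effect on the comparison is unknown, because no death or transfer rates are given. It is probably one or two points at most under the gaps assumed above, and it is a bias only if rates differ by site. Nothing in the documents shows that they do. If they did, one site per arm would leave no way to separate the difference from the intervention.

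Two stronger readings are tempting and not supported:

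- **That patient movement is scored as treatment failure.** The outcome is a continuous proportion, only days after the missed scheduled date count, and viral load is a separate outcome.
- **That a modest site difference would look highly significant.** A gap of 6 points in exits (2% against 8%, both assumed) is large against a person-level standard error of √(2 × 0.05 × 0.95 / 8,000) = 0.34 points. That ignores clustering. With the plan's ICC of 0.05 the standard error is 0.34 × √200.95, about 4.9 points, and the gap is about 1.2 standard errors. How well the primary model reflects between-site variation is a separate question.

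**What to change.** 1. In Section 10 (Objective 2), end observation at the date of death or of any documented transfer to another facility, or define catchment area so that this follows.
2. Prespecify a sensitivity analysis under the current rule. It needs a definition of catchment area and a record of whether the receiving facility lies inside it.
3. Analyse each patient at the site where they were active at study start. Remove duplicate entries where the patient ID allows it; the documents do not say whether the ID carries over between facilities in the de-identified extract.
4. Add patient status (active, died, transferred out, abandoned) with its date to Appendices 9 and 10.
5. Report deaths and transfers by site.

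The cost is a sentence or two and a few more fields from the electronic system that already supplies the extract. Undocumented moves will still count as lost. The rule should be settled before outcome data are seen, since choosing it afterwards would be post hoc.

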## 6. Design and Study Questions

We propose to conduct a pilot cluster randomized controlled trial to evaluate the effects of our interventions. Four health care facilities in Zambézia Province will be selected and then randomized to the control (standard-of-care [SOC]) or the intervention arms (anti-stigma training ONLY, resilience training ONLY, or anti-stigma + resilience trainings) (i.e., there will be one control arm and three intervention arms).

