## **Data Analysis**

### **Objective 1:**

#### Quantitative Data Analysis

We will first conduct descriptive analyses. Our psychological and psychosocial measures are continuous or pseudo-continuous (e.g., sums of Likert-style questions) variables. Our outcomes

will be changes in psychosocial measures from baseline to follow-up. Descriptive analyses will include boxplots and summary measures by intervention arm (4 groups). Our formal analyses (those that test hypotheses) will take advantage of the factorial nature of this pilot cluster randomized control trial. These analyses will group together sites as receiving resilience intervention (yes vs. no) and receiving anti-stigma intervention (yes vs. no); therefore, results from two sites will be compared with results from two other sites. This gives us a larger sample size for each comparison and allows us to fit linear mixed effects models that include random effects to account for the correlation between measurements taken from participants at the same site while ensuring that the fixed effect of the intervention is identifiable. We will report results from models that are unadjusted and adjusted for a small number of HCW-level baseline covariates (age, sex, HCW role, and baseline measures of the outcome). Model diagnostics will be performed and outcome variables will be transformed, if necessary, to meet model assumptions.

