$\text{logit}(P(Y \leq y)) = \beta_0(y) + \beta_1 \text{Intervention} + \beta_s \text{site} + \beta_x X$ , where  $\beta_1$  is the effect of the intervention on the log-odds ratio scale. Our primary objective is to test the null hypothesis,  $H_0: \beta_1 = 0$ . We will provide estimates of  $\beta_1$ , 95% Wald confidence intervals, and two-sided p-values. As with our other analyses, we will take advantage of the factorial nature of the model by grouping interventions as receiving resilience intervention (yes vs. no) and receiving anti-stigma intervention (yes vs. no). An interaction between the two interventions will also be assessed to see, for example, if the interventions are synergistic. The primary model will be adjusted for study site to acknowledge similarities between patients at the same site, and it will also be adjusted for a small number of patient-level baseline covariates, that are usually predictive of adherence to medications (e.g., age, sex, and education). In the model with the interaction between two interventions, study site will not be included so that the interaction effects are identifiable. In additional crude secondary analyses, we will investigate how changes in HCW measures correlate with patient outcomes by including average HCW metrics in models, replacing study site with this continuous variable. These latter analyses will be very much exploratory, as with only four study sites, we will have limited information to estimate these associations.

We will also compute three secondary measures of patient retention:

- (1) Monthly medication pick-up. Specifically, measured from the first day of ART initiation, any ART medication pick-up between days 16 and 45 will count as medication pick-up during month 1, any medication pick-up between days 46 and 75 will count as medication pick-up during month 2, and so forth, up until 6 months (i.e., medication pick-up between day 346 and 375); if the patient was enrolled on a three month pick up we will calculate on time pickups using the mark 15 days before and 15 days after the scheduled visit.

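### The model for proportion of time on medication contains both an intervention term and clinic fixed effects; with one site per arm, the intervention effect cannot be estimated or tested as written

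*Combined protocol and SAP*

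**What the plan says.** Section 6 randomises four facilities so that "there will be one control arm and three intervention arms", and Section 9 gives each arm one clinic.

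Section 10, Objective 2, sets out the analysis of the proportion of time on medication, which it treats as the main retention outcome: "Hence, we will fit a cumulative probability model (CPM) with fixed effects for the clinics". The equation models the cumulative logit as an intercept function plus β₁ × Intervention, plus a site term, plus patient covariates. The purpose is explicit: "Our primary objective is to test the null hypothesis" that β₁ is zero, reported with an estimate, "95% Wald confidence intervals, and two-sided p-values". The site term is confirmed a few lines later: "The primary model will be adjusted for study site to acknowledge similarities between patients at the same site". Intervention is coded factorially, as resilience yes/no and anti-stigma yes/no.

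The plan recognises identifiability in two other places. For the interaction model: "In the model with the interaction between two interventions, study site will not be included so that the interaction effects are identifiable". For the Objective 1 linear models it chooses random site effects, "while ensuring that the fixed effect of the intervention is identifiable".

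**The concern.** An intervention effect can be separated from fixed clinic effects only if intervention status varies within at least some clinics. Here it never does. The outcome is one proportion per patient over the six-month follow-up, and the model has no pre-intervention period that could supply within-clinic variation. The plan removes site from the interaction model for this reason but keeps it in the main-effect model, where the same obstacle applies.

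Section 8b lists this outcome first among the patient effectiveness measures, and Section 12 says the data will inform a fully powered trial. An analyst following the text will get an error, a dropped intervention term, or a precise-looking number whose value depends on an unstated coding choice.

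**Working it through.** **Inputs.** Four sites, one per arm (Sections 6 and 9): control (C), anti-stigma only (A), resilience only (R), both (AR). From Section 7c, Objective 2: m = 4,000 per site, two-sided α = 0.05, ICC 0.05 (also 0.025 and 0.10), 80% power, detectable difference 0.64 SD (also 0.45 and 0.91). ICC 0.001 below is an added assumption. SD units are carried over to the log-odds model as an approximation.

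**1. The plan's power figure.** For two sites against two, SE = √{2[1 + (m − 1)ICC] / (2m)}. At ICC 0.05 the design effect is 1 + 3,999 × 0.05 = 200.95, so SE = √(200.95/4,000) = 0.224 and the detectable difference is 2.80 × 0.224 = 0.628 SD. At ICC 0.025 and 0.10 it is 0.445 and 0.887 SD. These are close to the stated 0.64, 0.45 and 0.91. One site against one would need 0.888 SD at ICC 0.05. The stated figure thus counts between-site variation as error, with a normal reference. A model with fixed site effects does not.

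**2. Identification.** The resilience indicator equals the R dummy plus the AR dummy; the anti-stigma indicator equals A plus AR.
- Intercept, one factor, three site dummies: 5 columns, rank 4.
- Intercept, both factors, three site dummies: 6 columns, rank 4.

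Adding any constant to β₁ and subtracting it from the R and AR site effects leaves every fitted probability unchanged. In one simulated data set (four sites of 1,000), four choices of which site dummies to keep gave β₁ = 0.267, 0.489, 0.608 and 0.829 (SE about 0.08). All had log-likelihood −6977.367, the same as the model with site alone.

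**3. What a forced fit estimates.** Enumerating the full-rank codings obtained by dropping site columns, the resilience coefficient is:
- with one factor in the model: R − C, AR − C, R − A or AR − A;
- with both factors: R − C or AR − A.

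Under the null at ICC 0.05, the median spread among the possible answers is 0.47 SD (67% of draws disagree in sign) with one factor, and 0.30 SD (50%) with both.

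**4. Error rate of a forced fit.** A one-site contrast has true variance 2[ICC + (1 − ICC)/m], but the Wald variance is 2(1 − ICC)/m. The ratio is V = 1 + m·ICC/(1 − ICC), and the actual type I error is 2[1 − Φ(1.96/√V)].

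| ICC | V | Type I error |
|---|---|---|
| 0.001 (assumed) | 5.0 | 38% |
| 0.025 | 103.6 | 85% |
| 0.05 | 211.5 | 89% |
| 0.10 | 445.4 | 93% |

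At ICC 0.05 the Wald half-width is 1.96 × √(2 × 0.95/4,000) = 0.043 SD, while the contrast's null SD is √2 × 0.224 = 0.317 SD.

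**5. Alternatives.**
- *Delete site, keep patient-level Wald inference.* V becomes 1 + 3,999 × ICC, and type I error is 84.5%, 89.0% and 92.2% at the plan's three ICCs.
- *Both factors from four site values, 1 df.* The critical t is 12.706 and the noncentrality for 80% power is 16.33. At ICC 0.05 the detectable difference is 16.33 × 0.224 = 3.66 SD; power at 0.64 SD is about 18%. This assumes no interaction. With a 0.64 SD interaction, type I error falls to about 1.8%, and power at an average effect of 0.64 SD to about 6.5%.
- *One factor, 2 df.* At ICC 0.05, power at 0.64 SD is about 36% if the other intervention has no effect, 27% if its effect is 0.2 SD, and 1.8% if it is 0.64 SD.
- *Interaction model.* Four parameters on four sites leave no between-site degrees of freedom.

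**The case against.** The best defence is that factorial grouping puts two sites at each level of each factor. That helps a model with random site effects, but not this one: each site still has a single value of each factor, so intervention remains a function of site. Patient covariates do not change that. Nor can the site term be read as random, because the text says fixed effects and the plan distinguishes the two under Objective 1.

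Several qualifications do stand.
- The error rates are conditional. If software stops or drops the intervention term, no false result is reported. The ICCs are unsourced planning values; smaller ones give lower, though still badly inflated, rates.
- A reader might infer that a forced fit always yields one of four contrasts. That holds only with one factor in the model; with both there are two.
- A reader might infer that the trial's main tests all fail. The documents do not support this: the named co-primary outcomes are health care worker resilience and HIV stigma, and these and the other mixed-model outcomes use random site effects, so they are not aliased.
- The protocol calls itself a pilot and concedes in Sections 8a and 12 that four sites are a limitation. That tempers the consequences, but it is a statement about power and does not disclose that this model cannot be estimated.

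**Conclusion.** The point holds for this cumulative probability model and must be fixed before analysis. Non-identification follows from the plan's equation and one site per arm; it needs no ICC or other assumption. The type I error of about 85% to 93% is a secondary result. It assumes a forced fit, 4,000 patients per site, Section 7c's ICCs and a linear approximation, and should not be quoted as the trial's false-positive rate.

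It would also be too strong to say that only one replacement is valid. The 1-df, 2-df and random-site analyses trade assumptions against power, and the documents do not settle the choice.

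**What to change.** In Section 10, Objective 2:
1. Do not fit the intervention term and clinic fixed effects together. Fit the model with site and patient covariates, report the four adjusted site log-odds, and form the two factorial main-effect contrasts from them, labelled descriptive pilot evidence.
2. Do not merely delete site and keep patient-level Wald inference, since that ignores clustering. For the same reason, report the interaction descriptively.
3. If a formal interval or test is kept, base it on between-site variation with few degrees of freedom and state its assumption: no interaction for the joint 1-df analysis, a negligible effect of the other intervention for the one-factor 2-df analysis. A random site intercept, as under Objective 1, would also restore identification but still needs a small-sample method.
4. In Section 7c, state that 0.64 SD is close to a normal-reference value for two sites against two and does not describe this analysis.

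The cost is plan wording, model code and a revised power statement; no new data are needed. The price is very wide intervals (on 1 df at ICC 0.05, about 12.706 × 0.224 = ±2.8 SD with the site-level SD at its assumed value) and no interaction p-value.

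### The primary adherence model tests one training at a time beside fixed clinic effects, so its coefficient cannot be estimated as printed, and neither obvious way of fitting it reliably isolates one training

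*Combined protocol and SAP*

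**What the plan says.** Section 6 randomises four facilities, one to each of control, anti-stigma only, resilience only and both trainings.

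For proportion of time on medication, Section 10 (Data Analysis, Objective 2) says "we will fit a cumulative probability model (CPM) with fixed effects for the clinics". The printed formula has a threshold intercept, one intervention term, a site term and patient covariates. Its b1 "is the effect of the intervention on the log-odds ratio scale", and the primary null hypothesis is b1 = 0. The plan adds: "The primary model will be adjusted for study site to acknowledge similarities between patients at the same site".

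The factorial structure is used by "grouping interventions as receiving resilience intervention (yes vs. no) and receiving anti-stigma intervention (yes vs. no". Under Objective 1 the same device is described as one in which "results from two sites will be compared with results from two other sites". The CPM is also introduced with the remark that "in the absence of covariates, it reduces to the Wilcoxon rank sum test", which describes a comparison of two groups.

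The clinic terms come out in one place only: "In the model with the interaction between two interventions, study site will not be included so that the interaction effects are identifiable". The plan does not say whether the main-effect model for one training contains the indicator for the other.

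On clinic size, Section 9 states "Health facilities will be eligible for selection in the study if they serve at least 4,000 patients enrolled on ART". Table 5 lists eight eligible facilities with 4,149 to 12,580 patients in the second quarter shown. The four to be used are not named.

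**The concern.** A factorial trial is meant to separate two effects. Section 12 gives identifying which training, or which combination, works best as the reason for the design. Proportion of time on medication is among the primary effectiveness measures for patients (Section 8b).

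The main-effect test as printed does not achieve that separation. The coefficient to be tested cannot be estimated beside the clinic terms, so the analyst will have to change the model after the data arrive. The plan does not say how, and with one indicator the available changes give different quantities. Some of them attribute part or all of one training's effect to the other.

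The continuous outcomes analysed by mixed models are largely spared, because a random clinic effect makes the clinic weights nearly equal. The point is specific to the CPM.

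**Working it through.** **Inputs.** Four clinics, one per arm (Section 6). Model terms from Section 10, Objective 2. Table 5 second-quarter counts: 12,580; 7,637; 6,981; 6,030; 5,917; 4,727; 4,422; 4,149. ICC 0.025 to 0.10 and n = 4,000 per clinic (Section 7c). The effect sizes used below, the six-level simulated outcome and the allocation of clinics to arms are assumptions.

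**1. The plan's own figure.** Section 7c gives a detectable difference of 0.64 SD at ICC 0.05. For two equal clinics against two, the standard error in SD units is sqrt(ICC + (1 - ICC)/n) = sqrt(0.05 + 0.95/4,000) = 0.224. Multiplying by 1.960 + 0.842 = 2.802 gives 0.628 SD, and power at 0.64 SD is 0.81. The figures at ICC 0.025 (0.45 SD) and 0.10 (0.91 SD) also reproduce, with power 0.81 and 0.82. So the power statement assumes equal clinics and counts between-clinic variance.

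**2. The model as printed.** Intercept, intervention and three clinic dummies make 5 columns. Four clinics give only four distinct rows, and the rank is 4. Intervention equals the sum of the indicators of its two trained clinics. Patient covariates do not break that dependence, so b1 is not identifiable.

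**3. Route A: drop clinic, keep one indicator.** Patients now carry equal weight. On the linear scale, the share of the anti-stigma effect that enters the resilience coefficient is

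share = n_both/(n_both + n_R) - n_S/(n_S + n_control).

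- Equal clinics: 1/2 - 1/2 = 0.
- Largest case (control 12,580; S 4,422; R 4,149; both 7,637): 7,637/11,786 - 4,422/17,002 = 0.648 - 0.260 = 0.388.
- All 70 × 24 = 1,680 choices and allocations, absolute share: median 0.133, 90th percentile 0.286, maximum 0.388; above 0.10 in 61%.
- Without the 12,580-patient facility (840 allocations): median 0.080, maximum 0.261; above 0.10 in 42%.
- Four smallest facilities only: maximum 0.105.

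Simulation check, one dataset per layout, with true resilience effect 0 and anti-stigma log-odds ratio 0.5. With control 7,637, S 4,422, R 4,149 and both 12,580, the share is 0.752 - 0.367 = 0.385, which predicts 0.385 × 0.5 = 0.19. The one-indicator fit gave 0.201 (SE 0.022). With both indicators it gave 0.009 (SE 0.024). With four clinics of 4,000 the two fits gave -0.044 and -0.046 (SE 0.029 each), so they agree, and both lie within sampling error of zero.

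**4. Route B: software drops an aliased clinic column.** Then b1 for resilience is a contrast of two single clinics:

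| b1 becomes | Multiple of anti-stigma effect carried |
|---|---|
| R minus control | 0 |
| both minus S | 0 |
| both minus control | +1 |
| R minus S | -1 |

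Which one appears depends on the reference clinic and the dropped column. Clinic size plays no part.

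**5. Both indicators.** Intercept, R and S without clinic terms is estimable and has no carry-over under additivity. Adding three clinic dummies gives 6 columns and rank 4, so the second indicator helps only if the clinic terms come out.

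**6. What this does not repair.** On a latent logistic scale (an assumption), the between-clinic SD is sqrt(ICC/(1 - ICC) × π²/3): 0.29, 0.42 and 0.60 log-odds at ICC 0.025, 0.05 and 0.10. A contrast of two clinics with two, weighted equally, has at least that standard error, against a model-based value near 0.024. In a clinic-level approximation over the Table 5 allocations (resilience effect 0, anti-stigma 0.5), the false-positive rate for resilience is about 91% at ICC 0.05 and just under 90% at ICC 0.025, with little difference between one indicator and two.

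**The case against.** Three things can be said for the plan.

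First, a reader might infer that unequal clinic sizes bias the primary analysis as it stands. They do not. The printed model has fixed clinic effects, and with those in place size does not weight b1. The carry-over in step 3 belongs to a model the analyst would reach by deleting the clinic terms. This objection stands and limits the point. It does not rescue b1, which cannot be estimated with those terms present.

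Second, the grouping sentence names both trainings and the next sentence considers their interaction, so both indicators in one main-effects model may be what was meant. That is possible. But the formula has one intervention term, there is one null hypothesis, and the remark about the rank sum test describes two groups. The wording is at best ambiguous; if both indicators were intended, the change only states it.

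Third, a reader might infer that a training with no effect would be declared significant purely because the other one worked. The documents do not support that. The small standard errors come from simulations without between-clinic variation, whereas Section 7c assumes an ICC of 0.025 to 0.10. At ICC 0.05 the largest carry-over, 0.388 × 0.5 = 0.19, is less than half of the 0.42 in step 6. It is a bias in the estimate. The dominant threat to the p-value is unmodelled clinic variation, and that remains after the second indicator is added.

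The plan also calls the trial a pilot and says four sites are inherently limiting. That tempers the consequence but does not settle which model will be fitted.

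**Conclusion.** The point holds in a limited form. The primary CPM has one intervention term beside fixed clinic effects and is not identifiable as printed. With one indicator, dropping clinic carries over a median of 13% and at most 39% of the other training's effect in absolute size. Letting software drop an aliased column carries over none or all of it, with either sign.

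The percentages assume that the analysed numbers resemble the Table 5 second-quarter counts and that every choice and allocation is equally likely. They are a range, since the four clinics are not named, and they shrink if the largest facility is not selected. Under additivity, both indicators without clinic terms remove the carry-over. No claim about significance or p-values follows from these figures.

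**What to change.** In Section 10, Objective 2:

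- Write the main-effect CPM with two indicators, resilience (0/1) and anti-stigma (0/1), plus the patient covariates, and remove the fixed clinic terms from it. Both changes are needed together.
- Test each coefficient adjusted for the other, and state that each main effect assumes additivity.
- Label comparisons that pool two clinics against two on one factor as descriptive.
- State how between-clinic variation enters the inference, or state plainly that it does not and that the model-based standard errors and p-values are therefore too small.

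The first three items need a few lines of wording and no new data. In the simulated cases the model-based standard error rises by up to about 9% (0.022 to 0.024). The fourth is the harder part. With four clinics and three clinic-level parameters (intercept and two trainings), 4 - 3 = 1 degree of freedom remains between clinics, so any honest allowance will be imprecise.
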